Digital Health Application for Training and Support of Elder Caregivers
CLARE Mobile App

Document Date: January 29, 2024

NCT05877586

Purpose of the Study

Our proposed pilot will investigate the feasibility of using a digital health application, Communication, Learning, Advocacy, Resources and Expertise (CLARE), in training and support of family and friends (i.e., caregivers) of older adults, many of whom are elders themselves. Our training and support will focus on discharge care of patients including early mobility, and self-care among caregivers through walking activities. We have three study aims: (1) to test the feasibility of CLARE in caregiving training and support during the early days of hospital discharge; (2) to use the Unified Theory of Acceptance and Use of Technology behavioral framework (UTAUT) to determine factors that will promote intent and use of CLARE among elder caregivers; and (3) (exploratory) - to explore preliminary efficacy of CLARE in improving caregiving preparedness to inform effect size and variability in outcome for our future work.

Background & Significance

In 2020, of the 53 million reported caregivers in the U.S., more than 10 million (19%) were aged 65 and above. Approximately two-thirds of individuals who required home caregiving (care-recipients) were older adults. Caregivers are considered the bedrock of homecare. Caregiving responsibilities are particularly heightened after hospital discharge when disease symptoms linger, and new care plans are initiated. Caregiving is critically important for older adults whose functional capacity is easily compromised due to hospitalization. Of approximately 33 million admitted to hospitals in 2020, 36% were older adults. The surge in technology has allowed healthcare to treat many chronic conditions in ambulatory settings. This means hospital admissions are reserved only for the sickest of sick. As the health acuity of admitted patients increases, upon discharge, their home caregivers will inevitably face more complex caregiving responsibilities. Yet, discharge practices have not changed much in more than three decades. Many hospitals still rely on patient/caregiver bedside teaching conducted mostly by nurses whose time and attention are understandably focused on caring for those still acutely ill. As a result, bedside discharge teaching has often been described as limited or rushed and many caregivers are left unprepared for their home caregiving responsibilities. Inadequately prepared caregivers often experience high levels of caregiving stress and often neglect their self-care. When caregivers are ill-prepared for their caregiving role, it places their loved ones at high risk to receive inappropriate care. The increasing complexity in home caregiving and the rising number of caregivers create an impetus to discover new approaches to support and train caregivers. Our prior studies show that caregivers benefited from enhanced support and training for discharge care through increased levels in caregiving preparedness. However, our face-to-face approach in our studies hindered our ability to reach many caregivers, especially those with disproportionate numbers of negative social determinants of health such as living in rural areas, lack of access to transportation, and lack of leave opportunities at work. One viable solution to maximize reach and access to programs is the use of technology. In 2021, we piloted a virtual program for Covid caregivers using an embedded video training link sent by email. However, only 54% of caregivers viewed our video. Most admitted that they were too preoccupied with patient care and household tasks to check emails. Rather, we noted caregivers responded quickly to text messages. Based on this experience and the extant literature on use of phone applications in patient care management, our team built CLARE, a digital health application that offers training and support to Covid caregivers.

Design & Procedures

Each caregiver will receive a unique invitation code to use the CLARE app. Our team will guide the caregiver through features of the application including how to complete demographics questionnaire and surveys for caregiving preparedness, and how to reply to reminders. CLARE will feature materials on hospital discharge preparation, Covid care, and caregiver self-care, all vetted by the DUHS Patient and Family Education department. Existing teaching on Covid covers isolation; quarantine; home sanitization; and monitoring for Covid symptoms such as cough, fever, fatigue, and shortness of breath. Content will be reviewed and amended to reflect the latest CDC guidelines for Covid care at the time of pilot implementation. CLARE will also include reminders on examining the After-Visit-Summary to determine home medications and information on follow-up appointments with patient's primary care providers. For caregiver support, we have included self-care strategies to manage anxiety and stress. For this pilot, we will add two modules. The first additional module will pertain to the importance of early mobility of patients with instructions on how to assist based on functional capacity: independent, partial assistance, dependent. For example, for physically independent patients, we will provide progressive distance walking activities from Day 1 to Day 7 (e.g., walking to sitting at the dining table to eat meals on Day 1 to walking around neighborhood as tolerated on Day 7). For patients needing partial assistance, we will include body mechanics for caregivers as they assist patients during walking or from sitting to standing. And, for physically dependent patients, CLARE will provide teaching on passive range of motion for early day of discharge to progress to active range of motion. The second additional module will be for caregiver self-care. We will include the importance of walking and provide daily reminders for activities that will involve walking. CLARE will provide caregiver training and support up to 7 days after hospital discharge. Seven days is intentional as post-hospital clinic visit frequently happens within this period where formal handoff of care from hospital to primary care occurs. We will push daily task reminders in the morning followed by words of encouragement in the afternoon to hopefully sustain caregivers' motivation to continue using CLARE. We will encourage caregivers to use CLARE's chat functionality to communicate with our team ad lib. We will promptly document and forward all medical questions to our hospital collaborators that include physicians, nurses, case managers, and physical/occupational therapists.

Selection of Subjects

To be eligible, caregivers must be the primary person who will aid patients at home after hospital discharge. Caregivers must be at least 35 years of age and provide care to a loved one who is also 55 years and above. Caregivers must possess a smart phone or a tablet.

In identifying subjects, we will implement the same process that we had used in our recent Covid caregiver training project. Our team will review patient roster at DUH at least twice weekly to identify patients, 55 years and above, admitted for Covid-related issues. Using the hospital text-messaging system, we will send text to corresponding admitting providers that we will call the emergency contact of patient as indicated in the patient's chart to determine if this person is the patient's caregiver. In the text to providers, we will provide a call back number and inform the provider that if we do not hear back

from them within 24 hours, that we will proceed with making the telephone call. During our engagement call, we will verify if the emergency contact person is the patient's caregiver. In our previous caregiving trial on Covid, an overwhelming majority of emergency contact people were found to be patients' caregivers themselves. If the emergency contact person is the patient's caregiver, our team will ascertain that the caregiver is 35 years and above, and able to speak and read in English, and possess a smart phone. If yes to all, we will describe the study and allow caregiver to ask questions. If interested in participating but still undecided, we will plan for a follow-up call within 24 hours. If interested and ready to participate, we will obtain verbal consent.

If the emergency contact person is not the patient's caregiver, we will ask the person if she/he knows of patient's caregiver. If yes, we will leave our contact telephone number with the emergency contact person to share with this caregiver. When the caregiver calls us, we will follow the same engagement/recruitment process described above.

Subject Recruitment and Compensation

Subject recruitment will follow the same workflow used in our recent Covid caregiver trial. Hospital providers will use the caregiver consult template we developed in Epic once they have ascertained the presence of a caregiver on an elder patient admitted with a Covid diagnosis and planned discharge home. The consult template includes data points to collect caregiver names and contact information. Once our team receives the consult via Epic's System List, our team will contact the caregiver by phone to assess eligibility and interest in participation. If interested, we will obtain verbal consent by phone. To begin caregiver training, the caregiver will receive an SMS link and/or e-mail to download the digital health application on their own smartphone or tablet.

Consent Process

Primary caregivers are individuals who have the capacity to provide assistance and care to patients (their loved ones) after hospital discharge. These are the caregivers that we will recruit to this pilot study. Thus, we do not anticipate any individuals with diminished capacity to be enrolled to our study.

Risk/Benefit Assessment

All recruitment procedures will comply with HIPAA and will receive approval from the Institutional Review Board at Duke University Medical Center. The consent process informs participants about the study, indicates the participation is voluntary and that he or she has the right to stop at any time. Risks are enumerated in the informed consent form and described orally during the consent process. Agreed wording for key messages during participant interactions, role plays, and explanatory materials will be developed. Recruitment and retention will be monitored; recruitment strategies will be adjusted in response to problems identified. Patients of all caregiver participants will continue to receive standard care provided by their health care providers at Duke University Hospital. Potential participants who

meet eligibility criteria will be provided with written materials describing the study, its purposes, and its requirements. A member of the research team will conduct informed consent and explain all study procedures.

Efforts will be made to reduce inconvenience to participants by scheduling assessments at times that are most convenient to them. Participants will be informed that they can withdraw from the study at any time for any reason. Protection of confidentiality will be accomplished by assigning each participant a distinct research code number and using this code number rather than the person's name on all documents and electronic data acquired from the individual. Should there be hard copies containing data acquired from participants, they will be kept in locked files at the study site, and only this project's staff will have access to these files. No name or other unique identifiers will be included in any of the datasets used in the planned analyses of this project. The names, addresses, telephone numbers and other identifying information that correspond to study codes will be stored in a separate secured file. Access to this master file will be limited to study personnel on a "need to know" basis. All research staff will sign a statement of confidentiality indicating that all participant information is not to be discussed outside of the research setting. Importantly, all aspects of the trial that involve confidential patient information will be managed in accordance with HIPAA requirements.

Study's participants will be caregivers (family and friends), 35 years and above, who will be the primary sources of assistance and care of elder patients with Covid at home after hospital discharge. Therefore, we will not be recruiting children, pregnant women, prisoners, or cognitively impaired individuals.

There are several potential benefits to study participants. First, as the US population continues to age and survivorship from chronic diseases increases, the number of individuals living at home who require assistance will rise as well. Many of these caregiving responsibilities are assumed by the family and friends of these individuals. Without appropriate training and support provided to their caregivers, patients are at risk of receiving suboptimal care. Additionally, lack of preparedness in caregiving has been associated with a high degree of stress among caregivers. If successful, this pilot may provide another approach to support and training caregivers. Second, if deemed feasible, this caregiver app may augment discharge practices offered by hospitals in the country. With the average hospital days of care trending down in the past years, the care that patients need to promote recovery will be passed on to their caregivers. Thus, better trained and supported caregivers may lead to less adverse events happening after hospital discharge that may result in a decrease in avoidable healthcare utilization. Third, without support, many caregivers are at much higher risks to experience anxiety, depression, and burden. Providing training and support to caregivers during periods when caregiving is particularly challenging, such as during the hospital to home discharge, may mitigate some of the risks associated with psychological distress.

If found feasible, the use of technology in caregiver support and training (i.e., CLARE app) has the potential to enhance access to valuable information and resources in home care. Better prepared caregivers in caregiving may lead to decrease in avoidable adverse events among patients after hospital discharge and may also promote caregiver well-being.

Data Analysis & Statistical Considerations

The proposed sample size of 50 is not based on formal power analysis, but a reasonable sample size to assess the feasibility of the intervention, the primary goal of the trial. This sample size should also be adequate to estimate the effect size and variation in outcomes that we need for future clinical trial planning. For this pilot, our quantitative variable for analysis is caregiving preparedness.

Below describes our statistical plan and design related to the project aims.

Aim 1: Feasibility of CLARE. Among eligible caregivers we have a goal of at least 60% enrollment rate. Among participants, we will examine engagement in CLARE by assessing the percentage of daily completed tasks. We expect a minimum 60% completion rate per daily task for each caregiver.

Aim 2: Intent and use of CLARE. Using Nvivo, we will look for themes of modifiable factors that can be enhanced to facilitate use of CLARE and barriers that can be eliminated. We will explore differences in themes of responses by caregiver gender and levels of experience and comfort in technology. To ensure credibility and dependability of analyses, two team members will perform thematic analysis. For validation, another team member will read 20% of transcripts.

Aim 3 (exploratory): Impact of CLARE: We will calculate Cohen's d in change in efficacy outcome between baseline and end of study participation in preparedness score in caregiving. We will also estimate the variability in change in this outcome, which can be used for power analysis for future efficacy testing in a randomized clinical trial. We will also assess the percentage of daily completed tasks in caregiver self-care and expect a minimum 60% completion rate per daily task for each caregiver.

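### Does Aim 1 need a written rule for turning each caregiver's 60% task completion into one engagement result for the cohort?

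*Combined protocol and SAP*

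**What the plan says.** The section Data Analysis & Statistical Considerations calls the sample of 50 "a reasonable sample size to assess the feasibility of the intervention, the primary goal of the trial", and says it does not come from a formal power calculation. Aim 1 then gives two feasibility yardsticks.

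- **Enrollment:** "Among eligible caregivers we have a goal of at least 60% enrollment rate". This is a cohort-level target with a named denominator.
- **Engagement:** "Among participants, we will examine engagement in CLARE by assessing the percentage of daily completed tasks", followed by "We expect a minimum 60% completion rate per daily task for each caregiver".

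Aim 3, labelled exploratory, repeats the engagement yardstick for another set of tasks: the "percentage of daily completed tasks in caregiver self-care and expect a minimum 60% completion rate per daily task for each caregiver".

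Two other sections bear on who is counted. Under Subject Recruitment and Compensation, verbal consent comes first; then "the caregiver will receive an SMS link and/or e-mail to download the digital health application on their own smartphone or tablet". Under Risk/Benefit Assessment, "Participants will be informed that they can withdraw from the study at any time for any reason". Design & Procedures limits support to at most 7 days after discharge and says the team will walk each caregiver through the app. The number of tasks per day is not stated.

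**The concern.** The engagement sentence can be read in two ways. Taken literally, all 50 caregivers must reach 60% on every task, so one non-user defeats it. Taken as naming the unit to which 60% applies, it defines an engaged caregiver but does not say how many engaged caregivers are enough. On neither reading does the plan say whether results are pooled or counted per caregiver, whether unused days after withdrawal are in the denominator, or whether a consented caregiver who never downloads the app scores zero or is left out.

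Non-use is not fanciful. Of the team's earlier emailed training, Background & Significance reports: "However, only 54% of caregivers viewed our video". Feasibility is the primary goal and engagement is one of only two yardsticks for it. If the summary were chosen after the data were seen, the same data could be described as meeting or missing expectations.

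**Working it through.** The plan gives no calculation to reproduce.

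**Inputs from the documents:** 50 caregivers, a 60% level, at most 7 days. **Assumptions of this check:** one task on each of 7 days, and the completion patterns below.

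**1. Caregiver-level threshold.** 0.60 × 7 = 4.2, so a caregiver needs 5 of 7 days (71.4%).

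**2. Can summaries disagree?** Pooled completion = total days completed / (50 × 7). Share reaching 60% = caregivers with at least 5 days / 50.

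| Pattern | Pooled completion | Share reaching 60% |
|---|---|---|
| 40 at 5/7, 10 at 0/7 | 200/350 = 57.1% | 40/50 = 80% |
| 25 at 7/7, 25 at 4/7 | 275/350 = 78.6% | 25/50 = 50% |

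They can disagree in either direction. The exact 95% interval for 40/50 is 66.3% to 90.0%.

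**3. Does the denominator matter?** Suppose 50 consent, 5 never download, 35 complete 6/7 and 10 complete 1/7. Days completed = 35 × 6 + 10 × 1 = 220.

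- Pooled, all consented: 220/350 = 62.9%. Pooled, downloaders: 220/(45 × 7) = 69.8%.
- Share reaching 60%, all consented: 35/50 = 70% (exact 95% CI 55.4% to 82.1%). Among downloaders: 35/45 = 77.8% (62.9% to 88.8%).

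All four summaries lie above 60%. One lower confidence limit is below 60% and the other above it, but that is not a conflict with the plan. The plan's 60% is a completion level within a caregiver; it sets no 60% share of caregivers and no rule based on confidence limits.

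**4. Does withdrawal handling matter?** A caregiver who completes 3 of 3 days and then withdraws scores 3/3 = 100% on days in the study, or 3/7 = 43% on all planned days. That one caregiver crosses the 60% line.

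**5. Is the literal reading plausible?** With independent days and a common daily completion probability p, the chance that one caregiver reaches 5 of 7 is P(X ≥ 5), X ~ Binomial(7, p). The chance that all 50 do is that value to the power 50.

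| p | One caregiver | All 50 |
|---|---|---|
| 0.80 | 0.852 | 0.0003 |
| 0.90 | 0.974 | 0.27 |
| 0.95 | 0.996 | 0.83 |

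A requirement that fails almost surely at 80% daily completion is unlikely to be what the authors meant. The wording agrees: enrollment is given a goal, while engagement is something the team expects.

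**6. Can ordinary reporting close the gap?** Let n_k be the number of consented caregivers completing k of 7 days. Pooled completion = Σ k·n_k / 350, and the share reaching 60% = (n_5 + n_6 + n_7)/50. Both follow from one table of eight counts per task. Removing the non-downloaders from n_0 and from the denominator gives the downloader versions; listing days in the study for those who withdrew gives both scores in step 4. Nothing in this depends on a rule fixed in advance.

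**The case for a change.** The strongest argument for a change is that feasibility is the primary goal, the fix would cost only a few words, and an expectation that can be called met or missed from the same data gives little help in judging the app feasible. The Risk/Benefit section does look ahead to such a judgement. Steps 2 and 4 show that the choice can move a result across 60%, and nothing in the documents stops that choice being made late.

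Part of this stands. The cohort summary, the task-day denominator and the withdrawal rule are unwritten, and naming them beforehand would be tidier.

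The rest is weaker. The denominator is not wholly absent: engagement is measured among participants, in contrast with eligible caregivers for enrollment, and because consent precedes the app link, participants most naturally means those who consented. Near-zero probabilities for all 50 passing show that the literal reading is impractical; they show no harm under the sensible one. The 54% viewing figure is a poor guide to non-use here: it came from an emailed link, the same paragraph says caregivers answered texts quickly, and CLARE comes with guided onboarding.

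A written rule would also settle less than it seems to. The decisive number, the share of caregivers required, would be left blank because the documents give no basis for it. Counting every occasion after withdrawal as not completed is one defensible choice among several, and tasks that stop applying for other reasons, such as readmission, would need their own rule. Setting a required share in Aim 3 would put a pass mark on an exploratory aim.

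**Conclusion.** The omission is real, but it is a gap that analysts can fill sensibly, and the plan need not change. In a descriptive pilot of 50 with no formal power basis and no decision tied to the engagement figure, the sound report is the distribution of completion per task among all consented caregivers and the number reaching 60%, with non-downloaders and withdrawals shown openly. Readers can then see any disagreement between summaries.

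The ambiguity is not trivial. In a constructed case it separates 57% pooled completion from 80% of caregivers reaching the level; in another, the choice of denominator moves the share from 70% to 78%. These sizes rest on an assumed single daily task over 7 days and invented completion patterns.

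The conclusion rests on reading the sentence as a caregiver-level expectation and participants as consented caregivers. It would differ if the plan tied progression to a later trial to a single engagement figure; it does not. The enrollment yardstick is unaffected, and the repeated sentence in Aim 3 can stay descriptive.

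### Aim 3's single-arm pre-post Cohen's d cannot supply the between-group effect size that the plan says the pilot will give for future trial planning

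*Combined protocol and SAP*

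**What the plan says.** The design has one arm. Under Design & Procedures: "Each caregiver will receive a unique invitation code to use the CLARE app". No control group, randomization or external comparator is described anywhere.

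The Purpose of the Study gives the third, exploratory aim as "to explore preliminary efficacy of CLARE in improving caregiving preparedness to inform effect size and variability in outcome for our future work". Data Analysis & Statistical Considerations says of the 50 caregivers: "This sample size should also be adequate to estimate the effect size and variation in outcomes that we need for future clinical trial planning". It then adds: "For this pilot, our quantitative variable for analysis is caregiving preparedness".

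The analysis is in the paragraph for Aim 3, marked exploratory and headed *Impact of CLARE*, which reads: "We will calculate Cohen's d in change in efficacy outcome between baseline and end of study participation in preparedness score in caregiving". The same paragraph adds a plan to "estimate the variability in change in this outcome, which can be used for power analysis for future efficacy testing in a randomized clinical trial". So the future trial is a randomized one, and the sentence that mentions its power analysis draws only on the variability of change.

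No section says that the pre-post d is not a between-group effect, and none says which SD it is divided by.

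**The concern.** A randomized trial is sized on the difference between arms. A one-arm change contains any CLARE effect plus whatever would have happened without the app: the first days of hands-on caregiving, ordinary discharge teaching, answering the same questionnaire twice, and regression to the mean. The documents themselves point to such background change. The Background says "Many hospitals still rely on patient/caregiver bedside teaching conducted mostly by nurses", and the Risk/Benefit Assessment says "Patients of all caregiver participants will continue to receive standard care".

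Preparedness is the only quantitative variable named for analysis, so this d is the only effect size the plan will produce. A later team that takes the purpose statement and the sample-size paragraph at face value would enter it as the between-group effect. If preparedness also rises under standard care, the randomized trial can then be too small. The heading *Impact of CLARE* encourages that reading. An unnamed standardizer makes the number harder still to reuse.

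**Working it through.** **The plan's own figure.** The sample size of 50 is stated without a power calculation. There is no alpha, power, effect size or SD to reproduce.

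**What d estimates.** Let the mean change with CLARE be Δ, and let a share s of it be change that would occur without CLARE. The between-group difference is Δ(1 − s), while the pre-post d standardizes Δ. The two agree only if s = 0, and a single arm carries no information on s. A larger sample narrows the interval around Δ and leaves s unknown.

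**Assumed inputs (none is in the documents).** Pre-post d = 0.5; two-sided alpha 0.05; 80% power; 1:1 allocation; s = 25% or 50%; baseline-to-end correlation r between 0.3 and 0.8; equal SDs at baseline and end wherever r is used. A two-sample t-test for d = 0.5 needs 63.8, so 64 per arm. That is the trial a team would plan from this d. A normal-approximation routine gives 63, 112 and 252 per arm where the t-test gives 64, 113 and 253; nothing turns on the difference.

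**(a) d on the SD of change; the future trial compares change scores.** True d = 0.5(1 − s).

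| s | True d | Power with 64 per arm | Needed per arm for 80% |
|---|---|---|---|
| 25% | 0.375 | 56% | 113 |
| 50% | 0.25 | 29% | 253 |

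**(b) Same d; the future trial uses ANCOVA.** Effective d = 0.5(1 − s)·√(2(1 − r)) / √(1 − r²). For example, s = 25% and r = 0.5 give 0.375 × 1 / 0.866 = 0.433.

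**(c) d on the baseline SD; ANCOVA.** Effective d = 0.5(1 − s) / √(1 − r²).

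Power with 64 per arm:

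| Case | s | r = 0.3 | r = 0.5 | r = 0.7 | r = 0.8 |
|---|---|---|---|---|---|
| (b) | 25% | 74% | 68% | 63% | 60% |
| (b) | 50% | 41% | 37% | 33% | 32% |
| (c) | 25% | 60% | 68% | 84% | 94% |
| (c) | 50% | 31% | 37% | 50% | 65% |

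In case (c) with s = 25%, power reaches the planned 80% once r is about 0.66 or more. It is still below what it would be with s = 0 (84% against 98% at r = 0.7), but the trial would not be underpowered.

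**Standardizer.** A change of 0.5 baseline SDs, divided by the SD of change, is 0.5 / √(2(1 − r)): 0.42, 0.50 or 0.65 for r = 0.3, 0.5 or 0.7. The same data give different values of d depending on a choice the plan does not state.

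**Precision with 50 complete pairs.**
- d: the noncentral-t 95% CI around an observed 0.5 is 0.20 to 0.79. Taken as a between-group effect, those limits mean about 380 down to 26 per arm, before any bias is considered.
- SD of change: √(49/χ²) with 49 degrees of freedom gives 95% limits of 0.84 to 1.25 times the estimate. Squared before rounding, these are 0.70 to 1.55 times in required sample size.
- Mean change: the 95% half-width is 2.01 / √50 = 0.28 SD of change.

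The sample can therefore describe variability usefully, which supports that half of the adequacy sentence.

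**The case against.** The harm needs a step that the documents do not take. No section says the pre-post d will be entered as the between-group effect, and the one sentence on powering the randomized trial relies on the variability of change, which is sound. Aim 3 is marked exploratory, its wording shows that the measure runs from baseline to end, and no test or success threshold rests on it. The background-change argument is partly inferred: the standard-care sentence is about patients, the bedside-teaching sentence is about hospitals in general, and the timing of the baseline survey relative to teaching is not given. Every input to the power figures is assumed, and the results run from 29% to 94%. Cases (b) and (c) also size the trial for a t-test and then analyse it by ANCOVA.

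Much of this stands, and it limits the weight of the point. It does not remove it. The sample-size paragraph lists effect size beside variation as something the pilot is adequate to estimate for trial planning, and the design cannot deliver that. Even if bedside teaching came before the baseline survey, time and caregiving experience would remain in the change score. Because s is unknown, the power figures show how the error could act; they do not predict a loss.

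**Conclusion.** The concern holds. The claim that 50 caregivers suffice to estimate the effect size for a future trial is wrong as written when the trial is randomized, because the only effect size produced is a one-arm pre-post change. The claim about variability is sound.

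The size depends on the share of change that would occur without CLARE, on the standardizer and on the future analysis. Under the assumptions above, a trial planned for 80% power could have as little as 29%, or could keep 80% or more. If preparedness fell without CLARE, the error would run the other way. The weight is minor to moderate: the aim is exploratory, and the feasibility results and the conduct of the pilot are unaffected. The correction is still worth making, because informing later planning is this number's stated purpose.

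**What to change.** 1. **Aim 3.** Replace the heading with *Within-group change in caregiving preparedness*. Report the mean change with its 95% CI, and name the standardizer of any d.
2. **Sample-size paragraph.** Limit the adequacy sentence to the variability of the outcome and give its precision, for example: with 50 complete pairs, the 95% limits for the SD of change are about 0.84 to 1.25 times the estimate, and the mean change is estimated to within about 0.28 SD of change. Add that the pre-post d will not be used as a between-group effect and that the target difference of a future trial will be justified separately.
3. **Purpose of the Study.** Align the wording of the third aim with this.
4. **Reporting.** Give the baseline SD, end SD, SD of change and baseline-to-end correlation, so that a later trial can be sized for change scores or ANCOVA.

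The cost is wording in three places and a few summaries of data already planned, with no extra participants, visits or instruments. The downside is that the pilot can no longer be presented as giving an efficacy effect size.
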